Appendix D. List of Abbreviations

Abbreviation	Definition
AE	adverse event
AESI	adverse event of special interest
AGN	Allergan
ATC	Anatomical therapeutic chemical
BCVA	best corrected visual acuity
CAE	controlled adverse environment
DED	dry eye disease
DMC	data monitoring committee
DMC	data monitoring committee
ECG	electrocardiogram
eCRF	electronic case report form
ETDRS	Early Treatment Diabetic Retinopathy Study
IOP	intraocular pressure
ITT	Intent-to-Treat
MedDRA	Medical Dictionary for Regulatory Activities
NEI	National Eye Institute
ODS	Ocular Discomfort Scale
PCS	potentially clinically significant
PK	pharmacokinetic
PT	preferred term
SAP	statistical analysis plan
SD	standard deviation
SOC	system organ class
TEAE	treatment-emergent adverse event
TESAE	treatment-emergent serious adverse event
WHO	World Health Organization

Appendix E. Changes to Protocol-planned Analyses

No statistical comparisons/tests among the study intervention groups will be performed for the safety data.

Safety Statistical Analysis Plan

2012-201-005 [Stage 1]

Title Page

Protocol Title:

A Multicenter, Vehicle-controlled, Double-Masked, Randomized Study to Evaluate the Safety, Tolerability, Pharmacokinetics, and Exploratory Efficacy of AGN-242428 and AGN-231868 in Participants with Dry Eye Disease

Protocol Number: 2012-201-005 [Stage 1]

Compound Number: AGN-242428 and AGN-231868

Short Title:

Safety, Tolerability, Pharmacokinetics, and Efficacy of AGN-242428 and AGN-231868 in

Participants with Dry Eye Disease

Sponsor Name: Allergan Sales LLC

Legal Registered Address: [name]

Regulatory Agency Identifier Number(s)

Registry ID

IND 139391, 139392

Table of Contents

Title Pag	Je	
Table of	Contents	2
List of T	ables	3
SAP Vei	rsion History	4
1.	Introduction	
1. 1.1.	Objectives and Endpoints	
1.2.	Study Design	
2.	Statistical Hypotheses	8
3.	Sample Size Determination	9
4.	Analysis Sets	10
5.	Statistical Analyses	11
5.1.	General Considerations	
5.2.	Participant Disposition.	12
5.3.	Primary Endpoint(s) Analysis	
5.4.	Secondary Endpoint(s) Analysis	13
5.5.		13
5.6.	Safety Analyses	13
5.6.1.	Extent of Exposure	13
5.6.2.	Adverse Events	14
5.6.2.1.	Adverse Events of Special Interest	15
5.6.3.	Additional Safety Assessments	16
5.6.3.1.	Clinical Laboratory Parameters	16
5.6.3.2.	Potential Hy's Law	17
5.6.3.3.	Vital Signs	17
5.6.3.4.	Electrocardiogram	18
5.6.3.5.	Physical Exam.	19
5.6.3.6.	Best-corrected Visual Acuity	19
5.6.3.7.	Intraocular Pressure	20
5.6.3.8.	Biomicroscopy	20
5.6.3.9.	Dilated Fundus Examination.	21
	Drop Tolerability Questionnaire Score	
5.7.	Other Analyses	
5.7.1.	Other Variables and/or Parameters	22
5.7.1.1.	Pharmacokinetic Analyses	22
5.7.2.	Subgroup Analyses	
5.8.	Interim Analyses	22
5.8.1.	Data Monitoring Committee	22

Safety Statistical Analysis Plan

2012-201-005 [Stage 1]

6.	Supporting Documentation	23				
6.1.	Appendix 1: List of Abbreviations					
6.2.	Appendix 2: Changes to Protocol-planned Analyses					
6.3.	Appendix 3: Supporting Study Information					
6.3.1.	1. Demographics					
6.3.2.	Baseline and Disease Characteristics					
6.3.3.	Protocol Deviations.	27				
6.3.4.	Medical and Ophthalmic History					
6.3.5.	Prior/Concomitant Medications (Including Dictionary)					

1.1. Objectives and Endpoints

Table 1-1 Stage 1 Objectives

Stage 1
Primary Objectives:

- To evaluate the safety and tolerability of up to three dose strengths of AGN-242428 and AGN-231868 and their respective vehicles in participants with dry eye disease (DED)
- To characterize the plasma and tear pharmacokinetics of AGN-242428 and AGN-231868 in participants with DED following a single bilateral administration; and 13 days of twice daily administration followed by a single administration to both eyes on the final day of administration

Objective Clinical Category	Statistical Category	Estimand/Variable
Safety	Primary	 Variables: Adverse events (AEs), clinical laboratory values, vital signs, electrocardiogram (ECG) findings, intraocular pressure (IOP), best-corrected visual acuity (BCVA), slit-lamp biomicroscopy, dilated fundus examination, Drop Tolerability Questionnaire score Population: Safety Population Analyses: Descriptive summary
Pharmacokinetics ^a	Primary	 Variables: Systemic and tear pharmacokinetic parameters Following a single dose administration: area under the plasma or tear concentration versus time curve from time 0 to time of the last measurable concentration (AUC_{0-tlast}) maximum plasma or tear drug concentration (C_{max}), time of maximum plasma or tear drug concentration (T_{max}), and terminal elimination half-life (t_{1/2}) Following repeat dose administration: area under the plasma or tear concentration versus time curve from time 0 to the end of the dosing interval (AUC_{0-τ}), C_{max}, T_{max}, minimum plasma or tear drug concentration at steady state (C_{min,ss}), accumulation index (AI), and t_{1/2} Population: Pharmacokinetics population Analyses: Descriptive summary

Note: All estimand attributes explicitly identified for primary estimands only.

^a Analyses of Pharmacokinetics data will be described in a separate Pharmacokinetic Data Analysis Plan.

Safety Statistical Analysis Plan

2012-201-005 [Stage 1]

1.2. Study Design

Study 2012-201-005 is a Phase 1/2a, multicenter, vehicle-controlled, double-masked, randomized study conducted in 2 consecutive stages in participants with DED. Stage 1 will be conducted at 1 to 2 sites in the United States.

Stage 1

Stage 1 will evaluate the safety, tolerability, and pharmacokinetics (plasma and tear), of a maximum of 3 dose strengths of AGN-242428 () and AGN-231868 () in up to 3 consecutive cohorts (1A, 1B [high dose], and 1C [mid dose]) of participants with DED. There will be 24 participants in each cohort, with participants in each cohort randomized into 1 of 4 intervention arms:

- AGN-242428 (N = 9)
- AGN-231868 (N = 9)
- AGN-242428 vehicle (N = 3)
- AGN-231868 vehicle (N = 3)

All participants will receive 1 drop of the assigned intervention administered by the site staff to the left eye on Day 1 (Visit 2). In the absence of significant study intervention-related safety findings from this administration at the site, on Days 2 to 14, the participants will self-administer a single drop to both eyes, twice daily. On Day 15 (Visit 5), the participants will be administered a single drop to both eyes by the site staff.

The sponsor will decide whether to proceed to the next cohort after DMC review of safety data. If no significant safety or tolerability findings are identified in Cohort 1B, Cohort 1C will not be initiated.

Stage 2

Analysis of Stage 2 data will be discussed in a separate SAP.

No participant can be enrolled in more than 1 cohort and/or stage of the study.

If all doses are well tolerated, the duration of participation for each participant in the study will be as follows:

• For participants in Stage 1: approximately 1 month (Day -14 through collection of the last PK sample on Day 15)

Safety Statistical Analysis Plan

2012-201-005 [Stage 1]

2. Statistical Hypotheses

No hypothesis testing will be performed for Stage 1 safety data.

Safety Statistical Analysis Plan

2012-201-005 [Stage 1]

3. Sample Size Determination

For Stage 1, the sample size is not based on statistical considerations and is determined empirically.

Safety Statistical Analysis Plan

2012-201-005 [Stage 1]

4. Analysis Sets

The analysis set for safety will consist of the population as defined below:

Table 4–1 Analysis Sets

Population	Definition	Study Intervention
Safety	All participants who received at least one administration of	Actual received
	study intervention for stage 1	

Safety Statistical Analysis Plan

CONFIDENTIAL AGN-242428 AGN-231868 2012-201-005 [Stage 1]

5. Statistical Analyses

5.1. General Considerations

The methodologies specified to individual variables are defined as follows:

Table 5-1 Statistical Methodology

Methodology	Description
Categorical descriptives	 Number and percentage of participants in individual categories ○ Participants with ≥ 1 qualifying event counted once per individual category
PCS descriptives	 Number and percentage of participants meeting potentially clinically significant (PCS) criteria ○ Participants with ≥ 1 qualifying event counted once per PCS category Percentage denominator = number of participants with available (non-missing) non-PCS baseline value(s) or available (non-missing) baseline and ≥1 non-missing postbaseline assessment ○ Unevaluable assessments considered missing
Continuous descriptives	 N1, mean, standard deviation (SD), Q1, Q3, median, minimum, maximum N1 = participants with non-missing value
CFB descriptives	 Continuous descriptives for baseline, postbaseline, and change from baseline (CFB) values N1 = participants with non-missing values at both baseline and the specified postbaseline analysis by visit/timepoint
Supportive data listing	 After table listings, i.e. the listing supports the findings from a table. Fully defined in the tables, figure, and listing specification document

CFB = change from baseline; PCS = potentially clinically significant; SD = standard deviation.

- An interim database lock will occur after completion of Stage 1. At the end of the study (completion of Stage 2), the final database lock will occur.
- All data will be provided in data listings which will be fully defined in the table, figure, and listing specification document. For these data listings, missing or incomplete dates or missing AE severity or relationship will be listed as is.
- The change from baseline values will be computed as the value for the post baseline visit minus the baseline value, unless otherwise indicated.
- Safety analyses will be based on the observed data. No imputation of missing values will be performed.

Safety Statistical Analysis Plan 2012-201-005 [Stage 1]

- Partial dates will be treated as missing in computations but will be listed in the data listings as they appear on the eCRFs unless otherwise specified. No imputation of missing values will be performed, unless otherwise specified.
- All statistical analysis will be performed using SAS version 9.4 or higher.
- MedDRA will be used to code adverse events and medical history.
- WHO Drug Dictionary will be used to code medications.
- Relative study day is defined as the number of days from the first dose date and will be presented in all data listings where a complete date is presented.
- The baseline for safety parameters will be the last assessment prior to the first administration of study intervention.
- Day 1 is the study day on which study intervention is first administered.
- The end of study for a participant is the last date that he/she participated in the study. The date will be captured on the end of intervention eCRF page.

5.2. Participant Disposition

Number of participants screened for the study will be provided.

For each cohort, summary of study disposition will be provided by study intervention for the following:

- Number of participants randomized
- Number of participants treated
- Number of participants that completed the study
- Number of participants discontinued from the study
- eCRF-reported discontinuation reasons

In addition, a listing will be provided for participant disposition.

Safety Statistical Analysis Plan

CONFIDENTIAL AGN-242428 AGN-231868 2012-201-005 [Stage 1]

Table 5-2 Participant Disposition Summaries

Parameter	Description	Timing	Methodology
Study disposition	Distribution in the Safety Population by study intervention for each cohort.	_	Categorical descriptives/ Supportive data listing

5.3. Primary Endpoint(s) Analysis

Not applicable.

5.4. Secondary Endpoint(s) Analysis

Not applicable.

5.5. Tertiary/Exploratory Endpoint(s) Analysis

Not applicable.

5.6. Safety Analyses

Safety analyses will be based on the Safety Population.

Baseline assessments for applicable safety parameters are defined as follows:

Table 5-3 Baseline Definitions

Parameter	Baseline definition
Clinical laboratory evaluationsVital signsECGs	Last non-missing assessment before the first dose for each participant in Stage 1
BCVA IOP	

5.6.1. Extent of Exposure

Exposure to the study treatment for the Safety Population will be summarized for treatment duration, calculated as last study intervention date - first study intervention date + 1. Descriptive statistics will be presented by cohort and study intervention group.

Safety Statistical Analysis Plan

2012-201-005 [Stage 1]

5.6.2. Adverse Events

An AE will be considered a TEAE if:

- The AE began on or after the first administration of study intervention, or
- The AE was present before the first administration of study intervention, but worsened (increased in severity or became serious) on or after the first dose of study intervention

An AE that occurs after the Exit or Early Termination visits will not be counted as a TEAE.

An AE will be considered a TESAE if it is a TEAE that additionally meets any SAE criterion.

TEAEs will be summarized by cohort and study intervention group using the Safety population.

If more than 1 AE is coded to the same preferred term for the same participant, the participant will be counted only once for that preferred term using the most severe and most related occurrence for the summarizations by severity and by relationship to study intervention.

Listings of all TEAEs, TESAEs, TEAEs leading to discontinuation by participant, and deaths will be presented.

AEs will be coded using MedDRA version 23.0 or newer. Unique participants reporting AEs in the following AE categories will be summarized by cohort and study intervention group for the Safety Population as follows:

Safety Statistical Analysis Plan

2012-201-005 [Stage 1]

Table 5-4 TEAE Summaries

Parameters	Description	Methodology
AE	Overall summary by cohort and study intervention group only for the following categories: TEAEs Treatment-related TEAEs TESAEs Treatment-related TESAEs TEAEs leading to study discontinuation Deaths	Categorical descriptives
TEAEs	Overall summary by cohort and study intervention group and by SOC and PT Participants categorized overall and within each SOC and PT in decreasing frequency	Categorical descriptives
TEAEs by severity	Overall summary by cohort and study intervention group and by SOC, PT, and severity • Participants categorized overall and within each SOC and PT in decreasing frequency for the most severe occurrence	Categorical descriptives
Treatment-related TEAEs	Overall summary by cohort and study intervention group and by SOC and PT • Participants categorized overall and within each SOC and PT in decreasing frequency	Categorical descriptives
TESAEs	Overall summary by cohort and study intervention group and by SOC and PT ^a	Categorical descriptives ¹ Supportive data listing
TEAEs leading to discontinuation	Overall summary by cohort and study intervention group and by SOC and PT ^a	Categorical descriptives ¹ Supportive data listing
AESI	Overall summary by cohort and study intervention group and by SOC and PT ^a	Categorical descriptives ¹ Supportive data listing

^a Create summary tables only if at least 5 participants reported SAE, AEs leading to study discontinuation or AESI.

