Participants in Cohort 1B will be randomized 3:3:1:1 to receive AGN-242428, AGN-231868, or their respective vehicles. The same dosing regimen used in Cohort 1A will be applied in Cohort 1B. If any significant safety findings are identified during dosing in Cohort 1B, the DMC can recommend proceeding to Cohort 1C. In Cohort 1C, participants will be randomized 3:3:1:1 to receive AGN-242428, AGN-231868, or their respective vehicles. The same dosing regimen used in the previous cohorts will be applied in Cohort 1C. If no significant safety or tolerability findings are identified in Cohort 1B (high dose), Cohort 1C (mid dose) will not be initiated. It is possible that only 1 of the 2 tested experimental interventions (AGN-242428 or AGN-231868) and corresponding vehicle will proceed to the next cohort following DMC review of safety data.

After the sponsor's determination of adequate safety and tolerability of the interventions in Stage 1, Stage 2 will begin. The AGN-242428 and AGN-231868 doses will be selected based on safety and tolerability assessed in Stage 1; ie, the highest safe and tolerated dose of each intervention will be selected for testing in Stage 2. It is possible that only 1 experimental intervention (AGN-242428 or AGN-231868) will have acceptable safety to proceed to Stage 2. All participants enrolled in Stage 2 will have DED. In addition, participants will be selected based on their response to the controlled adverse environment (CAE). Only participants with DED who respond to the CAE with an increase in the signs and symptoms of DED will be enrolled in Stage 2.

Number of Participants:

For Stages 1 and 2, the sample size is not based on statistical considerations and is determined empirically. Approximately 322 participants (72 in Stage 1 and 250 in Stage 2) will be enrolled in the study. Participants withdrawn due to adverse events (AEs) will not be replaced. Participants who are withdrawn for other reasons may be replaced at the discretion of the sponsor if deemed necessary. No participant can be enrolled in more than 1 cohort and/or stage of the study.

Number of Sites:

Stage 1 will be conducted at 1 to 2 sites in the United States and Stage 2 will be conducted at up to approximately 8 sites in the United States.

Intervention Groups and Study Duration:

Stage 1

Stage 1 includes up to 3 consecutive cohorts, with 24 participants in each cohort. Participants in each cohort will be randomized into 4 groups in a 3:3:1:1 ratio, as follows:

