- AGN-242428 (N = 9)
- AGN-231868 (N = 9)
- AGN-242428 vehicle (N = 3)
- AGN-231868 vehicle (N = 3)

Stage 2

250 participants who requalify at the Baseline visit will be randomized into 5 groups, in a 1:1:1:1:1 ratio within each site, as follows:

- AGN-242428 (N = 50)
- AGN-242428 vehicle (N = 50)
- AGN-231868 (N = 50)
- AGN-231868 vehicle (N = 50)
- Xiidra (N = 50)

Assuming no early termination, the duration of participation for each participant in the study will be as follows:

- Stage 1: approximately 1 month (Day -14 through collection of the last PK sample on Day 15)
- Stage 2: approximately 2.5 months (up to 14 days prior to Visit 2 on Day -14 through the last assessment on Day 42)

Data Monitoring Committee: Yes

[figure not shown]

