6.1. Study Intervention(s) Administered

Table 6-1 Study Interventions

Study Intervention Name	AGN-242428	AGN-231868	Xiidra	AGN-242428 vehicle	AGN-231868 vehicle	
Dosage Formulation	Ophthalmic solution	Ophthalmic solution	Ophthalmic solution	Ophthalmic solution	Ophthalmic solution	
Manufacturer	Allergan	Allergan	Shire	Allergan	Allergan	
Concentrations			5%	NA	NA	
Route of Administration	Topical eyedrop	Topical eyedrop	Topical eyedrop	Topical eyedrop	Topical eyedrop	
Dosing Instructions	Participants will be instructed to instill a single drop per eye, twice daily (approximately 12 hours apart) (with the exception of Day 1 in Stage 1 where only the left eye will be dosed once with a single drop and the last day of dosing in both stages where a single dose will be administered to both eyes). On visit days, the morning dose of the intervention will be administered by the site staff. More details on the dosing regimen can be found in Section 6.1.1.					

Packaging and Labeling

In Stage 1, AGN-242428, AGN-231868 and their vehicles will be provided in identical single-use bottles. In Stage 2, AGN-242428, AGN-231868 and their vehicles will be provided in identical single-use vials. Xiidra will be supplied in single-use, commercially available vials that will have the original label overlaid with a new clinical label to prevent unmasking.

All interventions

will be supplied in identical cartons.

All study interventions, including vehicles and marketed products, will be labeled with the protocol number, kit number, warning language (Caution: New Drug—Limited by Federal Law to Investigational Use. Keep Out of Reach of Children), and instructions to take as directed.

Immediately before dispensing the study intervention, the investigator (or appropriately trained designee) will write the participant number, and the date dispensed on the label.

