5.6.3.10. Drop Tolerability Questionnaire Score

Participants will be asked to rate the acute overall tolerability attributes of study interventions on an 8-question VAS Drop Tolerability Questionnaire. Descriptive statistics for each question at Baseline (Day 1), and changes from baseline at each postbaseline visit will be presented by cohort and study intervention group.

Table 5-16 Drop Tolerability Questionnaire Score

Parameter	Description	Timing	Methodology
Drop Tolerability Questionnaire VAS	Raw values and change from baseline	Treatment period	CFB descriptives
score			

Safety Statistical Analysis Plan 2012-201-005 [Stage 1]

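### Most Stage 1 safety tables show each vehicle at n = 3 per cohort, with no supplementary column pooling a compound's own vehicle across cohorts

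*SAP*

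**What the plan says.** Stage 1 SAP 5.6.2 sets the unit of tabulation for adverse events: "TEAEs will be summarized by cohort and study intervention group using the Safety population". The same split is set for laboratory values (5.6.3.1), vital signs (5.6.3.3), ECG (5.6.3.4), BCVA descriptive statistics (5.6.3.6), IOP (5.6.3.7) and biomicroscopy (5.6.3.8). For drop tolerability (5.6.3.10), the statistics for each question "will be presented by cohort and study intervention group". One exception is the vision-loss tabulation in 5.6.3.6, whose text gives study intervention group and eye without cohort.

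On numbers, the protocol Synopsis says "Stage 1 includes up to 3 consecutive cohorts, with 24 participants in each cohort" and "Participants in each cohort will be randomized into 4 groups in a 3:3:1:1 ratio", which it lists as 9, 9, 3 and 3. The third cohort is conditional (Stage 1 SAP 1.2): "If no significant safety or tolerability findings are identified in Cohort 1B, Cohort 1C will not be initiated". The Synopsis also allows one compound, with its vehicle, to drop out between cohorts. It applies the same dosing regimen in every cohort.

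The vehicles are part of the primary safety and tolerability objective (protocol 3.1; Stage 1 SAP Table 1-1). Protocol Table 6-1 has one column for each compound's vehicle, with concentration not applicable. Protocol 9.4.2.1 tabulates TEAEs by study intervention group and does not ask for a cohort split. The Stage 1 SAP text contains no pooled vehicle column and no pooling rule.

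**The concern.** Each dose column of 9 is read beside a vehicle column of 3. Three people say little about the background of adverse events or drop discomfort due to the vehicle, the instillation or the disease. A second or third cohort adds 3 more people per vehicle on the same schedule, but the planned tables never bring them together. Drop tolerability is where this matters most, because the reader wants to know how much stinging or blur comes from the vehicle and how much from the drug. Since the primary objective covers the vehicles as well as the actives, a summary that never describes a vehicle with more than 3 people uses less of the collected data than it could.

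**Working it through.** **Allocation.** The inputs are 24 per cohort, ratio 3:3:1:1 and up to 3 cohorts (protocol Synopsis).

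- Active: 24 × 3/8 = 9 per compound per cohort. Vehicle: 24 × 1/8 = 3 per compound per cohort.
- Total: 3 × 24 = 72, and 72 + 250 = 322. This matches the plan: "Approximately 322 participants (72 in Stage 1 and 250 in Stage 2) will be enrolled in the study".
- Pooled vehicle per compound: 3 + 3 = 6 after Cohorts 1A and 1B; 3 + 3 + 3 = 9 only if 1C also runs; 3 if the compound stops after 1A.

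There is no power or alpha to reproduce, because the sample size is empirical and Stage 1 safety has no hypothesis test.

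**Vehicle background, zero events.** The exact two-sided 95% upper limit for 0/n is 1 − 0.025^(1/n).

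**Active minus vehicle.** With a common SD and 9 on active, SE/SD = √(1/9 + 1/n). The same factor applies to a difference in rates if the event rate is common to both arms.

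**Vehicle alone.** Relative to n = 3, the SE is √(3/n).

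| Vehicle n | Upper limit, 0/n | SE of difference (SD units) | Change from n = 3 | Change in SE, vehicle alone |
|---|---|---|---|---|
| 3 | 70.8% | √(1/9 + 1/3) = 0.667 | – | – |
| 6 | 45.9% | √(1/9 + 1/6) = 0.527 | −21% | −29% |
| 9 | 33.6% | √(1/9 + 1/9) = 0.471 | −29% | −42% |

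**Illustration under assumed event rates.** The documents give no event rate, so 10% to 30% is an assumption. The approximate 95% half-width for active minus vehicle is 1.96 × √(p(1 − p)(1/9 + 1/n)). The chance of seeing at least one vehicle event is 1 − (1 − p)^n.

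| Assumed rate p | Half-width in percentage points, n = 3 / 6 / 9 | Chance of ≥ 1 vehicle event, n = 3 / 6 / 9 |
|---|---|---|
| 10% | 39 / 31 / 28 | 27% / 47% / 61% |
| 20% | 52 / 41 / 37 | 49% / 74% / 87% |
| 30% | 60 / 47 / 42 | 66% / 88% / 96% |

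The gain is largest for the vehicle background. It is smaller for the contrast with active, because each dose stays at 9.

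**The case against.** Several points against this are fair.

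- **Dose selection.** A reader might infer that thin vehicle columns undermine the choice of the Stage 2 dose. The documents do not support that. Protocol 9.5 says the analyses after the interim lock are not needed in order to proceed to Stage 2, and progression between cohorts rests on DMC review under a charter that is not part of these documents.
- **Vehicle identity.** A reader might take it as established that one and the same vehicle is used in every cohort. It is an inference from Table 6-1 and from the repeated reference to respective vehicles. The actives also have one column each in that table despite several strengths. The statement that "AGN-242428, AGN-231868 and their vehicles will be provided in identical single-use bottles" concerns packaging, not composition. Protocol 4.3 ties the top dose to formulation feasibility, so composition has to be confirmed.
- **No formal comparison.** Stage 1 is descriptive. No interval or difference is planned, all data are listed (Stage 1 SAP 5.1), and a reader can add adverse event counts across columns. So no power is lost. But adding columns by hand does not give a pooled mean, SD or median for tolerability, IOP or laboratory values.
- **Concurrent controls.** Cohorts are sequential, so pooled vehicle participants are partly non-concurrent. By-cohort tables preserve the randomized comparison and match the unit of DMC review. This is a good reason to keep them, but it does not rule out an added column.
- **Separate specifications and timing.** Table specifications sit in another document and might contain a pooled column, though the SAP text does not require one. Stage 2 SAP 10.0 says Stage 1 has been locked, unmasked and analysed. That limits how the column can be labelled. It does not remove its use, since a topline report replaced an interim CSR (Stage 1 SAP 5.8).

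**Conclusion.** The point holds as a matter of descriptive precision. Most Stage 1 safety summaries leave each vehicle at 3 participants per column, and no pooled column is planned in the SAP text. Pooling would lower the zero-event upper limit from 71% to 46% with two cohorts, or to 34% with three. It would cut the standard error of active minus vehicle by 21% or 29%.

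This rests on three assumptions: that each vehicle has the same composition across cohorts, that cohort or time effects are small, and that the compound continues past Cohort 1A. The figure of 9 is a maximum that needs Cohort 1C. If a compound stops after 1A, there is nothing to pool.

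Two stronger statements are tempting and go too far. One is that drug and vehicle effects cannot be separated at all. They are poorly separated at n = 3 and somewhat better at 6 or 9, and an upper limit of 46% or 34% still leaves the background rate poorly known. The other is that every Stage 1 summary is split by cohort, which the vision-loss text contradicts.

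**What to change.** 1. Confirm in one line, from the formulation records, that each compound's vehicle had the same composition in every cohort. If it did not, do not pool.
2. If it did, add for each compound one column pooling its own vehicle across the cohorts that were run, beside the dose columns. Do this in the AE, laboratory, vital signs, ECG, BCVA, IOP, biomicroscopy and drop tolerability tables. Do not combine the two compounds' vehicles.
3. Keep the by-cohort columns, so that concurrent randomized comparisons and any drift between cohorts stay visible.
4. Because Stage 1 is already locked and unmasked, label the column supplementary in the final reporting and say that it was added after unmasking.

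The cost is one extra column per compound and no new data. No error rate is affected, because no test is planned. The drawback is that the pooled column assumes no cohort or time effect, which the retained columns let the reader check roughly.
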